19.2. Treatment allocation

Following the implementation of protocol v6.0 whereby patients transfer to the non-randomised component of the trial, all participants will be allocated to receive pembrolizumab treatment in the therapeutic trial centrally by ICR-CTSU upon confirmation of a positive ctDNA result.

Prior to the implementation of protocol v6.0 during the randomised component of the trial, in the therapeutic component, participants were randomised between pembrolizumab treatment and observation (continued ctDNA surveillance) on a 2:1 basis. Treatment allocation is via a minimisation algorithm, balancing for time from trial entry to randomisation (0 months i.e. ctDNA detected in baseline screening sample vs. 3-12 months) and adjuvant capecitabine status (i.e. whether or not a patient received adjuvant capecitabine). Minimisation is a widely recognised method of ensuring balance between treatment groups for several prognostic factors in clinical trials with smaller sample sizes. Treatment allocation to the next participant enrolled depends on

the characteristics of the patients already involved, thus minimising the imbalance across the prognostic factors. To make the allocation of treatment more unpredictable, a random element was incorporated in the algorithm.

19.3. Endpoint definitions

19.3.1. **Primary Endpoints**

ctDNA surveillance

• Positive ctDNA detection by 12 and 24 months from start of ctDNA surveillance. This will be calculated as the proportion of patients with ctDNA positivity by each time point from those with assessment performed at that time point. Proportions will be presented with associated exact 95% confidence intervals.

Therapeutic component

 Absence of detectable ctDNA or disease recurrence 6 months (24 weeks) after commencing pembrolizumab. This will be calculated as the proportion of patients without either detectable ctDNA or disease recurrence 6 months after commencing pembrolizumab. Proportions will be presented with associated exact 95% confidence intervals.

19.3.2. Secondary Endpoints

Secondary endpoints relating to the observation group will be analysed in the patients randomised to the observation group prior to the implementation of protocol v6.0.

ctDNA surveillance

1) Time to ctDNA detection. This will be calculated as the time from entry into the ctDNA surveillance to first positive ctDNA detection. Statistical techniques for time to event data will be used to summarise data and display the pattern of ctDNA detection graphically.

Therapeutic component

- Detection of overt metastatic disease at the time of first ctDNA detection in patients allocated to pembrolizumab. This will be calculated as the proportion of patients with metastatic disease from CT scan at the same time point as first positive ctDNA detection, and presented with associated exact 95% confidence interval.
- 2) Lead-time between ctDNA detection and recurrence in the pembrolizumab treatment and observation groups. This will be calculated as the time between therapeutic trial entry and first confirmed detection of recurrent disease. Recurrence will include loco-regional and distant recurrence, but will exclude new primary cancers. Statistical techniques for time to event data will be used to summarise data and display time between ctDNA detection and recurrence graphically.
- 3) Absence of detectable ctDNA or disease recurrence after 6 months in the observation group. This will be calculated as the proportion of patients without either detectable ctDNA or disease recurrence 6 months after randomisation to the observation group. Proportions will be presented with associated exact 95% confidence intervals.
- **4)** Safety and tolerability of pembrolizumab in this patient group. Safety will be assessed throughout the treatment period using the NCI CTCAE v4.0 and summarised in tabular format. Reported toxicities

will be coded using Med DRA (current version). The proportion of patients reporting a dose reduction/delay during pembrolizumab will be presented.

5) Commencement of treatment in patients allocated to receive pembrolizumab. This will be calculated as the proportion of patients allocated to receive pembrolizumab who start this therapy. The proportion will be presented with associated exact 95% confidence interval.

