3.2.1. Pembrolizumab treatment group

If a patient is allocated to the pembrolizumab treatment group, the treating team will be informed by ICR-CTSU. If the patient is receiving adjuvant capecitabine or radiotherapy, they will be offered the option to join the therapeutic trial either by switching treatment from capecitabine to pembrolizumab, or commencing pembrolizumab in combination with radiotherapy. If the patient confirms their consent to receive trial treatment (including switching their treatment from capecitabine to pembrolizumab) staging scans should be done to detect for evidence of macroscopic disease, prior to commencing pembrolizumab. If macroscopic disease is detected, the patient will not receive pembrolizumab treatment and will instead receive standard treatment for recurrent disease outside of the c-TRAK TN trial. If there is no evidence of macroscopic disease, the patient should commence treatment with pembrolizumab treatment (200mg given intravenously every 3 weeks) for up to a maximum of 12 months or until unacceptable toxicity or withdrawal of the patient's consent for any reason (see section 11.6). No further imaging will be performed after commencing pembrolizumab unless clinically indicated, in which case local procedure should be followed. Patients who are diagnosed with disease recurrence must stop pembrolizumab, and should receive standard treatment for recurrent disease outside of the c-TRAK TN trial. Patients who present with isolated lymphadenopathy may continue pembrolizumab until relapse is confirmed, and should be managed as per section 13.1.

Patients who are allocated to pembrolizumab but do not wish to commence pembrolizumab treatment (including switching treatment from capecitabine to pembrolizumab), will not enter the therapeutic component of the c-TRAK TN trial and if agreed should instead continue with 3 monthly ctDNA surveillance. Blood samples for ctDNA analysis should continue to be collected during and after pembrolizumab treatment as described in section 11. The results of these ctDNA analyses will not be reported to the treating team or patient.

3.2.2. **Observation group (continued blinded ctDNA surveillance – prior to protocol v6.0)**

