Prior to the implementation of protocol v6.0 during the randomised component of the trial, if a patient was randomised to the observation group, the treating team and patient were **not** informed that randomisation had taken place in order to remain blinded to the positive ctDNA result the patient would continue to have blood samples collected for ctDNA analysis as described in section 8.

Following implementation of protocol v6.0, all patients who were previously randomised to observation and remain in ctDNA surveillance will transition to the non-randomised component of the trial following reconsent, and be allocated to pembrolizumab at the next positive ctDNA result.

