11.1. Pre-treatment assessments

The following pre-treatment assessments should be conducted once written informed consent to start **pembrolizumab has been obtained** from the patient and after the treatment eligibility checklist has been completed by the principal investigator (or designated investigator) and submitted to ICR-CTSU. The pre-treatment assessments should be done prior to the first dose of pembrolizumab treatment as below.

Assessments to be conducted within 4 weeks prior to starting treatment:

- Imaging to assess for macroscopic disease (using same modality as diagnosis). For example patients
 screened with CT and bone scan at diagnosis should have both repeated, or patients screened with
 FDG PET-CT at diagnosis should have a FDG PET-CT repeated. Patients who did not have imaging at
 diagnosis should have imaging in line with local guidelines for high risk disease
- ECG
- Demographics and baseline conditions

Assessments to be conducted within 72 hours prior to the first dose of pembrolizumab:

- Safety blood tests: clotting (INR or PT/ aPTT), haematology (ANC, platelets, haemoglobin), biochemistry; hepatic function (bilirubin, ALT, AST, ALP and GGT), renal function (serum creatinine or estimated GFR (using Cockcroft-Gault)), thyroid function (T3, T4, TSH), glucose (random)
- Urinalysis
- Female patients of childbearing potential should have a negative urine or serum pregnancy test. If the urine test is positive or cannot be confirmed as negative, a serum pregnancy test will be required
- Concomitant medication review
- Full physical examination (ECOG performance status, vital signs, height and weight)

- Research blood samples for ctDNA analysis:
 - o 2 x 10ml collected in ctDNA preservation tubes
- Research blood sample for PBMC (peripheral blood mononuclear cell) isolation (PBMC sites only)
 - 3 x 10ml collected in heparin tubes, to be couriered as soon as possible after collection, as per the c-TRAK TN Investigator Laboratory Manual

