- 3. Follow up bloods for patients who complete pembrolizumab or discontinue prematurely should be taken every 3 months in line with the start of ctDNA surveillance. For example if a patient goes on to receive treatment due to a positive ctDNA result at the 12 month ctDNA surveillance blood sample and then completes the full 12 months of pembrolizumab treatment, bloods will be taken at month 27, 30, 33, 36 and 39 from the start of ctDNA surveillance, and if a patient discontinues at month 7 bloods would be taken at month 21, 24, 27, 30 and 33 from start of surveillance
- 4. Written informed consent must be obtained from the patient prior to pre-treatment assessments being conducted.
- 5. Full physical examination includes height (prior to first dose of pembrolizumab only), weight (required prior to first dose of pembrolizumab and cycles 4, 8, 12 and 16 only), ECOG performance status and vital signs (heart rate, blood pressure).
- 6. Consent for imaging is included in registration PIS and ICF following implementation of protocol v6.0 onwards. Patients should undergo imaging immediately upon confirmation of a ctDNA positive result. The same investigations conducted as part of staging for the original primary breast cancer should be repeated. Patients who did not have imaging at diagnosis should have imaging in line with local guidelines for high risk disease.
- 7. Patients should be followed-up in line with standard practice every 6 months (+/- 1 month) from start of ctDNA surveillance. During post treatment follow up this can be conducted as a telephone call to the patient. Patients should be asked about relapse of breast cancer or other change in medical history. A recurrence tumour tissue sample should be provided at relapse for each patient who has tissue available from a biopsy taken routinely as part of standard patient care.
- 8. Pregnancy test should be done within 72hrs of first administration of pembrolizumab treatment.
- 9. With the exception of the end of treatment assessments, safety blood tests should be conducted within 72 hours prior to each cycle of pembrolizumab.
- 10. During pembrolizumab treatment, 2 x 10ml of blood should be collected in ctDNA preservation tubes on day 1 (pre-dose) of each cycle and until completion or withdrawal of pembrolizumab treatment. For 1 year after the administration of the last dose of pembrolizumab, 2 x 10ml of blood should be then collected every 3 months (+/- 2 weeks).

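### The overt-metastasis endpoint (Protocol 19.3.2, therapeutic item 1) is not aligned with the protocol's own staging rules on scan type, scan timing and who is scanned

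*Protocol*

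**What the plan says.** Section 19.3.2 names the endpoint as "Detection of overt metastatic disease at the time of first ctDNA detection in patients allocated to pembrolizumab" and says that it is "calculated as the proportion of patients with metastatic disease from CT scan at the same time point as first positive ctDNA detection", with an exact 95% confidence interval. It sets no target rate, test or decision rule.

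Other sections govern which scan is done, when, and in whom:

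- **Scan type.** Section 11.1 repeats the modality used at diagnosis. Patients "screened with CT and bone scan at diagnosis should have both repeated", and those screened with "FDG PET-CT at diagnosis should have a FDG PET-CT repeated". Note 6 to the schedule in section 11.7 likewise repeats the original staging investigations.
- **Scan timing and consent.** Under section 3.2.1, once the patient has confirmed consent to trial treatment, "staging scans should be done to detect for evidence of macroscopic disease, prior to commencing pembrolizumab". Section 11.1 also places imaging among the assessments done after treatment consent. Note 6 in section 11.7 instead says "Patients should undergo imaging immediately upon confirmation of a ctDNA positive result", with consent for imaging contained in the registration documents from v6.0.
- **Former observation patients.** Under sections 3.2 and 3.2.2, those still in ctDNA surveillance are to re-consent and "be allocated to pembrolizumab at the next positive ctDNA result". Sections 1.2.5 and 9 state that neither site nor patient was told of the first positive result.
- **Denominator.** For the first primary endpoint, section 19.3.1 takes the proportion "from those with assessment performed at that time point". Item 1 of section 19.3.2 has no such restriction.

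**The concern.** The endpoint shows how often disease is already visible on imaging when ctDNA first turns positive. It therefore bears on the first primary objective, which concerns residual disease not visible on imaging. Section 1.2.1 also gives overt metastatic disease being more frequent than predicted as one of the reasons for the v6.0 redesign, so the reported rate will be read closely.

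The definition fixes one modality, one time point and one population. The rest of the protocol does not guarantee that every patient in that population has that scan at that time. Some metastases found by the protocol's own staging fall outside the numerator, and some allocated patients have no scan that fits the definition.

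**Working it through.** The protocol gives no expected rate, number or precision for this endpoint, so there is no figure to reproduce. The likely number of patients can be checked against section 19.1: 150 × 0.30 = 45 ctDNA positive, and 45 × 2/3 = 30 allocated under the former 2:1 randomisation. Both match the table in section 19.1.2. Section 19.1.2 notes that closing randomisation may raise the number treated. With 30 to 45 patients, one misclassified patient moves the rate by 1/30 = 3.3 to 1/45 = 2.2 percentage points.

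**1. Scan type.** Sections 3.2.1, 9.2.1 (item 7) and 9.3 make a patient ineligible if staging shows disease, whichever scan shows it. Section 19.3.2 counts CT only. A patient with metastases seen only on bone scan is therefore excluded from treatment but absent from the numerator. If a share m of overt cases is visible only off CT, the observed rate is p(1 − m). With an assumed p = 30%:

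- m = 10%: 0.30 × 0.90 = 27%
- m = 20%: 0.30 × 0.80 = 24%

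This effect has one direction only.

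**2. Former observation patients.** They become allocated patients at a later positive result. Sampling is 3-monthly, so their staging scan comes about one interval or more after first detection. Those who relapsed meanwhile have left surveillance. If they form a share c of those allocated, and their later scan is positive at rate p_late, there are three cases. With assumed c = 20% and p = 30%:

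- counted as negative: (1 − c)p = 0.80 × 0.30 = 24%
- later scan used: (1 − c)p + c × p_late = 0.24 + 0.20 × 0.50 = 34%, or 0.24 + 0.20 × 0.70 = 38%, for p_late of 50% or 70%
- excluded: 30%, unchanged

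The direction depends on a rule that the endpoint definition does not state.

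**3. Allocated but unscanned patients.** Under sections 3.2.1 and 11.1 imaging follows treatment consent, and section 9.3 gives those who decline only ctDNA bloods and follow-up. If a share u is unscanned and stays in the denominator without being able to enter the numerator, the rate becomes p(1 − u). With p = 30% this is 27%, 24% or 21% for u = 10%, 20% or 30%. In whole patients, with 30 allocated and Clopper-Pearson intervals:

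| Unscanned | Among those scanned | Among all allocated |
|---|---|---|
| 6 (20%) | 7/24 = 29.2% (12.6 to 51.1) | 7/30 = 23.3% (9.9 to 42.3) |
| 9 (30%) | 6/21 = 28.6% (11.3 to 52.2) | 6/30 = 20.0% (7.7 to 38.6) |

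The values of p, m, c, p_late and u are all assumptions. None stands in the protocol.

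**The case against.** A reader might infer that former observation patients, unscanned decliners and all bone-scan or PET findings count as disease-free, so that the rate is understated. The protocol does not support that much.

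- It never says how an allocated patient without a scan is classified. Rules on missing assessments commonly sit in the statistical analysis plan, to which section 19.4 defers further detail.
- Former observation patients could push the rate either way or not at all. Even their membership of this endpoint is inferred from the allocation wording in sections 3.2 and 3.2.2.
- From v6.0, note 6 in section 11.7 allows imaging under registration consent at once after a positive result, so a patient who later declines treatment may already have been scanned.
- FDG PET-CT includes a CT component, so its findings are not all lost. The CT wording may be shorthand for staging scans in general.

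These points stand and limit the claim, but they do not remove it. The CT restriction is stated in the protocol and conflicts with its own imaging rule. An unrestricted denominator is a natural reading, because section 19.3.1 states an assessed-only denominator where one is meant. Section 19.4 also applies intention to treat to the therapeutic component, although its explanation names the primary endpoint. Note 6 does not cover patients who declined before v6.0, and it contradicts sections 3.2.1 and 11.1.

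**Conclusion.** The endpoint definition needs correcting. The CT-only numerator is a stated rule that, followed literally, omits disease seen only on bone scan, and it can only lower the rate. For former observation patients the definition cannot be met as written, since they had no protocol-triggered scan at first detection, and the direction of any bias is open. For decliners the denominator is unclear. The gap is plain before v6.0 and depends afterwards on which imaging passage is followed.

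A general statement that the rate is understated is not supported, and the size of any effect cannot be derived from the document. The percentages above show scale under assumed inputs only. This is a descriptive secondary endpoint with no decision rule attached. The point matters because the rate informs the first primary objective, and because a few patients among 30 to 45 shift it noticeably.

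**What to change.** In section 19.3.2, therapeutic item 1:

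- Replace the CT wording with: on any protocol staging imaging (CT, bone scan or FDG PET-CT).
- Define the denominator as patients staged after their first positive ctDNA result, and report beside it the number allocated but not staged. The staged-only rate assumes that unstaged patients resemble staged ones, so the count of unstaged patients is needed to judge it.
- Show former observation patients separately, with the interval from first positive result to scan.

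Sections 3.2.1 and 11.1 must also be reconciled with note 6 in section 11.7 on when imaging is done and under which consent.

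The cost is a change of wording and a few extra table rows. The denominator is slightly smaller and the interval slightly wider: in the illustration, 12.6 to 51.1% on 24 patients against 9.9 to 42.3% on 30.

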4.2. Secondary Endpoints

- 1) Time to ctDNA detection defined as time from entry into the ctDNA surveillance to first positive ctDNA detection.
- 2) Detection of overt metastatic disease at the time of first ctDNA detection in patients allocated to pembrolizumab.
- 3) Lead-time between ctDNA detection and disease recurrence in the pembrolizumab treatment and observation group.
- 4) Absence of detectable ctDNA or disease recurrence after 6 months in the observation group.
- 5) Safety and tolerability of pembrolizumab.
- 6) Commencement of treatment in patients allocated to receive pembrolizumab.

NB. Secondary endpoints relating to the observation group will be analysed in the patients randomised to the observation group prior to the implementation of protocol v6.0.

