19. STATISTICAL CONSIDERATIONS

19.1. Statistical design and sample size justification

19.1.1. Screening component

This consists of a single cohort who will have ctDNA surveillance every 3 months for 2 years. Patients who are found to be ctDNA positive within the first 12 months of ctDNA surveillance will enter the therapeutic trial. The size of the screening cohort has been chosen to anticipate the required number of patients eligible for the therapeutic trial (assuming 30% patients have a positive ctDNA during the first 12 months) and will provide further descriptive information relating to ctDNA incidence and lead time over detection of overt clinical relapse. The trial aims to recruit 150 patients into ctDNA surveillance. It is anticipated that approximately 75% of patients initially enrolled will be eligible for ctDNA surveillance, therefore approximately 200 patients will be recruited in total. The Independent Data Monitoring Committee (IDMC) will monitor the ctDNA positivity rate observed throughout the course of the trial and make recommendations regarding any increase or decrease in the overall size of the screening cohort based on this. All patients who enter the screening cohort will have the opportunity to enter the intervention phase if they become ctDNA positive within the first 12 months, regardless of the overall number of patients currently recruited to the therapeutic component of the trial.

If the incidence assumptions are correct and approximately 30% of patients have a positive ctDNA during the first 12 months of surveillance then 150 patients will enable the incidence of ctDNA positivity to be estimated with a two-sided 95% confidence interval of +/-7.3%.

In the original randomised trial design (prior to the implementation of protocol v6.0) the planned exploratory analyses were detailed as follows: Exploratory analysis will be performed comparing time to macroscopic relapse between two groups, 1) patients who remain ctDNA negative within the first 12 months and do not enter the therapeutic trial, and 2) patients who become ctDNA positive and are randomised to the observation group in therapeutic trial.

Subsequent to the removal of the randomised component (implementation of protocol v6.0) the above analyses will be amended to censor any patient who had been previously randomised to the observation group at the date they subsequently started pembrolizumab.

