19.3.3. Exploratory Endpoints

Exploratory endpoints relating to the observation group will be analysed in the patients randomised to the observation group prior to the implementation of protocol v6.0.

- 1) Descriptive differences in time between ctDNA detection and disease recurrence, and disease free survival, between patients in the pembrolizumab treatment and observation groups. The times from first ctDNA detection to disease recurrence, and to disease free survival event (i.e. including new breast primary cancer or breast cancer death) will be calculated using statistical techniques for time to event data and summarised for each randomised treatment group. This will be calculated and presented separately for the pembrolizumab and observation randomised groups, with patients included in their randomised group regardless of treatment actually received. If recurrence is confirmed after initial continuation of treatment for development of isolated lymphadenopathy, the date of first scan will be used in analyses as date of recurrence.
- 2) To explore predictors of sustained ctDNA clearance on pembrolizumab. The proportion of patients with absence of detectable ctDNA or disease recurrence 12 months after commencing pembrolizumab will be tabulated by clinical and biological factors of interest. Consideration will be given to the use of logistic regression to investigate relationships between factors considered and ctDNA clearance in univariate and multivariable models.
- 3) To explore potential predictors of relapse and ctDNA detection, and alternative definitions of ctDNA clearance. Lead time will be calculated as described previously. Statistical techniques for time to event data will be used to summarise lead time data and display graphical according to clinical and biological factors of interest. Alternative definitions of the proportion of patients without either detectable ctDNA or disease recurrence at 12 months, and other time points, after randomisation to the observation group. Proportions will be presented with associated exact 95% confidence intervals.

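### Lead time is named as ctDNA detection to recurrence but calculated from therapeutic trial entry, and a staging scan at first positive was triggered in the pembrolizumab group only

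*Protocol*

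**What the plan says.** The secondary objective in Protocol 2.2 is the median lead time from ctDNA detection to relapse in both groups. Section 4.2 lists the endpoint as "Lead-time between ctDNA detection and disease recurrence in the pembrolizumab treatment and observation group". Section 19.3.2 keeps that name but sets a different start: "This will be calculated as the time between therapeutic trial entry and first confirmed detection of recurrent disease". In 19.3.3, exploratory endpoint 1 uses "The times from first ctDNA detection to disease recurrence, and to disease free survival event", exploratory endpoint 4 also counts from first detection, and exploratory endpoint 3 reuses the 19.3.2 calculation.

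On imaging, section 3.2.1 requires that for patients allocated to pembrolizumab "staging scans should be done to detect for evidence of macroscopic disease, prior to commencing pembrolizumab". Sections 1.2.5 and 3.2.2 say that observation patients and their teams were kept blind to the positive result, so it prompted no scan.

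On observation patients who later receive pembrolizumab, section 19.1.1 amends one analysis to "censor any patient who had been previously randomised to the observation group at the date they subsequently started pembrolizumab". Exploratory endpoint 1 instead works "with patients included in their randomised group regardless of treatment actually received". The lead-time entry in 19.3.2 has no rule of its own.

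**The concern.** One named interval has two start dates within section 19.3. The 19.3.2 start is the later one, so an analysis that follows it literally understates lead time in every patient. Lead time over clinical relapse tells readers how long a window there is for treating minimal residual disease, and section 19.1.1 gives it as one of the things the screening cohort should describe.

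Entry itself is not well defined. Sections 3.2.1 and 9 say that patients who decline pembrolizumab, or decline to switch from capecitabine, do not join the therapeutic component. Section 19.1.2 says every ctDNA-positive patient is entered, and 19.4 keeps decliners in the intention-to-treat analysis.

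A second matter affects the comparison between groups. Recurrence can be found on the scan triggered by the first positive result only in patients allocated to pembrolizumab. Their lead-time distribution may therefore contain a block of values near zero that has no counterpart at the same point in the observation group.

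**Working it through.** The endpoint has no target, sample size or power figure, so there is no plan figure to reproduce. The check is a comparison of texts plus illustrations on the one benchmark the protocol gives.

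**1. Start dates side by side**
- 2.2 objective: ctDNA detection
- 4.2 endpoint list: ctDNA detection
- 19.3.2 name: ctDNA detection
- 19.3.2 calculation: therapeutic trial entry
- 19.3.3 exploratory 1 and 4: first ctDNA detection
- 19.3.3 exploratory 3: as in 19.3.2, so therapeutic trial entry

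The 19.3.2 calculation and the endpoint that borrows it are the exceptions.

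**2. Size of the origin shift**

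Inputs: the median lead time of 7.1 months from the 55-patient cohort in section 1.1; a lag of w weeks between draw and allocation. No turnaround is stated for surveillance samples, so w is an assumption.

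Lag in months = w × 7 / 30.4375; share lost = lag / 7.1.
- w = 2: 14/30.4375 = 0.460 months; 0.460/7.1 = 6.48%; 7.1 falls to 6.6
- w = 4: 28/30.4375 = 0.920 months; 13.0%; 7.1 falls to 6.2
- w = 6: 42/30.4375 = 1.380 months; 19.4%; 7.1 falls to 5.7

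For one subgroup the documents support the top of this range. Under 7.2.2 and 7.2.3 a registration sample can trigger allocation in patients who had already completed standard therapy. The personalised assay cannot exist until mutation analysis is done, which 7.1.1 puts at about 6 weeks from receipt of tissue and blood. Entry is then about 6 weeks or more after the draw, though 3.1 says that prior outside sequencing may shorten this.

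**3. Recurrences found on the trigger scan**

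Assume exponential lead time with median 7.1 months, and a share f of pembrolizumab-allocated patients with disease on the trigger scan, placed at time zero. Then S(t) = (1 − f) × 2^(−t/7.1), and setting S = 0.5 gives median = 7.1 × log2(2(1 − f)).
- f = 10%: 7.1 × log2(1.8) = 6.0 months
- f = 25%: 7.1 × log2(1.5) = 4.2 months
- f = 40%: 7.1 × log2(1.2) = 1.9 months
- f = 50%: 7.1 × log2(1.0) = 0

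The shares are assumptions. Section 1.2.1 says only that overt metastatic disease was more frequent than first predicted.

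**4. Crossover left uncensored**

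With rate λ = ln 2/7.1, a share c switching at s months, and hazard ratio h afterwards, for t > s: S(t) = (1 − c)e^(−λt) + c·e^(−λ(s + h(t − s))). For c of 25 to 50%, s of 3 to 6 months and h of 0.5 to 0.7, the observation median runs from 7.2 to 8.6 months. With h = 1 it stays at 7.1. All three inputs are assumptions.

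**The case against.** The case on the other side is substantial except on the origin itself. Several stronger readings are tempting and are not supported.

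- **That scan-found recurrences can arise in one group only.** This holds at the first positive. From protocol v6.0, re-consented observation patients are allocated at their next positive result (3.2.2), and imaging follows confirmation of a positive (11.7, note 6). Such findings can therefore occur there too, but later.
- **That scan timing means the interval is no longer the one named.** Recurrence on a trigger scan is still an interval from detection to recurrence. The asymmetry harms comparability and the reading as lead over clinical relapse; it does not move the start or the end.
- **That the plan refuses to censor crossovers.** Section 19.3.2 is silent, 19.4 leaves further method to the SAP, and the rules in 19.1.1 and 19.3.3 belong to other analyses.
- **That decliners have no start date.** That follows from 3.2.1 and 9, but not from 19.1.2 and 19.4. The fair charge is ambiguity.
- **That the overt-metastasis endpoint mixes in later scans.** Its wording requires "metastatic disease from CT scan at the same time point as first positive ctDNA detection", so a crossover's later scan does not meet it. Only the denominator is unclear.

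It is also fair that section 19.1.2 treats observation as a reference rather than a formal comparator, that overt disease at first detection is already a separate endpoint, and that exploratory endpoint 1 supplies a detection-based interval. However, exploratory endpoint 1 is summarised by randomised group, so on its wording it does not cover patients allocated without randomisation from v6.0.

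Finally, sampling every 3 months and recurrence follow-up every 6 months (8.1.3) make a shift of a few weeks modest. That imprecision is present under either start date, whereas the lag is a one-way shift that can be removed. Nothing shows that the lag differs between groups.

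**Conclusion.** The start-date contradiction stands in full and does not depend on any SAP. Followed as written, 19.3.2 understates lead time by the sample-to-allocation lag: 0.5 to 1.4 months, or 6 to 19% of the 7.1-month benchmark, if the lag is 2 to 6 weeks. That range is assumed for surveillance samples. About 6 weeks or more is grounded in the protocol for registration samples that await mutation analysis. The benchmark comes from a different, 55-patient cohort and serves only as a yardstick.

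The trigger-scan asymmetry at first positive is real and limits comparison of the two groups. Its size depends on a share the documents do not give. Crossover handling and the overt-metastasis denominator are points to clarify, not errors. The endpoint is secondary and descriptive, so the remedy is a correction of wording and reporting.

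**What to change.** In 19.3.2, and wherever lead time is reused (including exploratory endpoint 3), start the clock at the draw date of the first positive sample for every ctDNA-positive patient, including those who decline pembrolizumab. This also removes the dependence on what counts as entry. Use the same date for first detection in exploratory endpoints 1 and 4.

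State whether disease found on the trigger scan is a lead-time event. Report pembrolizumab-group lead time with and without those recurrences, and present the contrast with observation as descriptive.

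Two secondary clarifications:
- Apply the 19.1.1 censoring at pembrolizumab start to observation-group lead time, with the as-randomised result as a sensitivity analysis. Both are worth showing, because crossover depends on a further positive result and no macroscopic disease, so the censoring may be informative.
- Limit the overt-metastasis denominator to patients whose first positive triggered the staging scan.

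The cost is wording and one extra tabulation. Samples are already labelled with their collection date (section 7), and the staging scans are already required.
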